5.2.7.1.2 Serious adverse event

A serious adverse event (SAE) is defined as any AE, which fulfils at least one of the following criteria:

- results in death,
- is life-threatening, which refers to an event in which the patient was at risk of death at the time of the event; it does not refer to an event that hypothetically might have caused death if more severe,
- requires inpatient hospitalisation or prolongation of existing hospitalisation
- results in persistent or significant disability or incapacity,
- is a congenital anomaly / birth defect,
- is deemed serious for any other reason if it is an important medical event when based on appropriate medical judgement which may jeopardise the patient and may require medical or surgical intervention to prevent one of the other outcomes listed in the above definitions. Examples of such events are intensive treatment in an emergency room or at home for allergic bronchospasm, blood dyscrasias or convulsions that do not result in hospitalisation or development of dependency or abuse.

5.2.7.1.3 AEs considered “Always Serious”

In accordance with the European Medicines Agency initiative on Important Medical Events, Boehringer Ingelheim has set up a list of AEs, which by their nature, can always be considered to be “serious” even though they may not have met the criteria of an SAE as defined above.

The latest list of “Always Serious AEs” can be found in the eDC system. A copy of the latest list of “Always Serious AEs” will be provided upon request. These events should always be reported as SAEs as described in [Section 5.2.7.2](#).

Cancers of new histology and exacerbations of existing cancer must be classified as a serious event regardless of the time since discontinuation of the drug and must be reported as

described in 5.2.7.2, subsections “AE Collection” and “AE reporting to sponsor and timelines”.

5.2.7.1.4 Adverse events of special interest

The term adverse events of special interest (AESI) relates to any specific AE that has been identified at the project level as being of particular concern for prospective safety monitoring and safety assessment within this trial, e.g. the potential for AEs based on knowledge from other compounds in the same class. AESIs need to be reported to the sponsor’s Pharmacovigilance Department within the same timeframe that applies to SAEs, please see [Section 5.2.7.2.2](#).

The following are considered as AESIs:

- adverse events relating to gastrointestinal perforation
- bleeding
- hepatic injury.
- pathological findings identified on bone imaging
- stunted growth identified on dental imaging.

Hepatic injury

In this trial protocol, signs of hepatic injury are defined as:

- ALT and/or AST ≥ 8 fold ULN
- ALT and/or AST ≥ 3 fold ULN and total bilirubin ≥ 2 fold ULN*
- ALT and/or AST ≥ 3 fold ULN and unexplained INR $> 1.5^*$
- ALT and/or AST ≥ 3 fold ULN and unexplained eosinophilia ($>5\%$)*
- ALT and/or AST ≥ 3 fold ULN and appearance of fatigue, nausea, vomiting, right upper abdominal quadrant pain or tenderness, fever and/or rash

*in the same blood draw sample.

These lab findings constitute a hepatic injury alert and the patients showing these lab abnormalities need to be followed up according to the “DILI checklist” provided in the eDC system.

In case of clinical symptoms of hepatic injury (icterus, unexplained encephalopathy, unexplained coagulopathy, right upper quadrant abdominal pain, etc.) without lab results (ALT, AST, total bilirubin) available, the investigator should make sure these parameters are analysed, if necessary, in an unscheduled blood test. Should the results meet the criteria of hepatic injury alert, the procedures described in the DILI checklist should be followed.

5.2.7.1.5 Intensity (severity) of AEs

The intensity (severity) of the AE should be judged based on the following:

- Mild: Awareness of sign(s) or symptom(s) that is / are easily tolerated.
Moderate: Sufficient discomfort to cause interference with usual activity.
Severe: Incapacitating or causing inability to work or to perform usual activities.

In addition, the intensity (severity) of diarrhoea adverse events should be classified and recorded in the eCRF according to the Common Terminology Criteria for Adverse Events (CTCAE) version 5 on an additional diarrhoea adverse events eCRF [[R18-1357](#)]. See Table 5.2.7.1.5: 1. below.

Table 5.2.7.1.5: 1 CTCAE Categorization for diarrhoea

CTCAE Grade	Diarrhoea
1	Increase of <4 stools per day over baseline
2	Increase of 4 to 6 stools per day over baseline
3	Increase of ≥ 7 stools per day over baseline; incontinence
4	Life threatening consequences
5	Death

5.2.7.1.6 Causal relationship of AEs

Medical judgement should be used to determine the relationship between the adverse event and the BI investigational compound, considering all relevant factors, including pattern of reaction, temporal relationship, de-challenge or re-challenge, confounding factors such as concomitant medication, concomitant diseases and relevant history.

Arguments that may suggest that there is a reasonable possibility of a causal relationship could be:

- The event is consistent with the known pharmacology of the trial drug.
- The event is known to be caused by or attributed to the drug class.
- A plausible time to onset of the event relative to the time of drug exposure.
- Evidence that the event is reproducible when the drug is re-introduced.
- No medically sound alternative aetiologies that could explain the event (e.g. pre-existing or concomitant diseases, or co-medications).
- The event is typically drug-related and infrequent in the general population not exposed to drugs (e.g. Stevens-Johnson syndrome).
- An indication of dose-response (i.e. greater effect size if the dose is increased, smaller effect size if dose is reduced).

Arguments that may suggest that there is no reasonable possibility of a causal relationship could be:

- No plausible time to onset of the event relative to the time of drug exposure is evident (e.g. pre-treatment cases, diagnosis of cancer or chronic disease within days / weeks of drug administration; an allergic reaction weeks after discontinuation of the trial drug concerned).
- Continuation of the event despite the withdrawal of the medication, taking into account the pharmacological properties of the compound (e.g. after 5 half-lives).

- Of note, this criterion may not be applicable to events whose time course is prolonged despite removing the original trigger.
- There is an alternative explanation, e.g. situations where other drugs or underlying diseases appear to provide a more likely explanation for the observed event than the drug concerned.
- Disappearance of the event even though the trial drug treatment continues or remains unchanged.

5.2.7.2 Adverse event collection and reporting

5.2.7.2.1 AE Collection

The investigator shall maintain and keep detailed records of all AEs in the patient files.

The following must be collected and documented on the appropriate eCRF(s) by the investigator:

From signing the informed consent onwards until the individual patient's end of trial (= the End of Study (EoS) visit): all AEs (serious and non-serious) and all AESIs.

For roll-over patients, any (S)AE that occurred after start of treatment in the parent trial and is continuing up to Visit 1 of this extension trial, will be recorded as (S)AEs at Visit 1 of this trial with the same information as it was recorded in the parent trial. If this ongoing AE is an SAE, then the follow-up report will still be sent on the parent trial SAE form, no new SAE form is to be completed for the extension trial.

After the individual patient's end of trial:

The investigator does not need to actively monitor the patient for new AEs but should only report any occurrence of cancer and trial drug related SAEs and trial drug related AESIs of which the investigator may become aware of by any means of communication, e.g. phone call. Those AEs should be reported on the BI SAE form ([Section 5.2.7.2.2.](#)), but not on the eCRF.

Vital Status Data Collection

Patients who discontinue trial treatment prematurely, who agree to be contacted further but do not agree to physical visits, should be followed up as described in [Section 3.3.4.1](#), withdrawal from trial treatment. From then on until the individual patient's end of the trial the investigator must report any occurrence of cancer, report all deaths / fatal AEs regardless of relationship, and trial drug related SAEs and trial drug related AESIs the investigator becomes aware of.

5.2.7.2.2 AE reporting to the sponsor and timelines

The investigator must report SAEs, AESIs, and non-serious AEs which are relevant for the reported SAE or AESI, on the BI SAE form to the sponsor's unique entry point within 24 hours of becoming aware of the event, the country specific process will be specified in the ISF. The same timeline applies if follow-up information becomes available. In specific occasions, the investigator could inform the sponsor upfront via telephone. This does not replace the requirement to complete the BI SAE form.

With receipt of any further information to these events, a follow-up SAE form has to be provided. For follow-up information the same rules and timeline apply as for initial information. All (S)AEs, including those persisting after individual patient's end of trial must be followed up until they have resolved, have been assessed as "chronic" or "stable", or no further information can be obtained.

5.2.7.2.3 Pregnancy

In rare cases, pregnancy might occur in a clinical trial. Once a patient has been enrolled in the clinical trial and has taken trial medication, the investigator must report any drug exposure during pregnancy in a trial participant immediately (within 24 hours) by means of Part A of the Pregnancy Monitoring Form to the sponsor's unique entry point.

The outcome of the pregnancy associated with the drug exposure during pregnancy must be followed up and reported to the sponsor's unique entry point on the Pregnancy Monitoring Form for Clinical Studies (Part B).

[figure not shown]
The ISF will contain the Pregnancy Monitoring Form for Clinical Studies (Part A and B).

[figure not shown]
As pregnancy itself is not to be reported as an AE, in the absence of an accompanying SAE and / or AESI, only the Pregnancy Monitoring Form for Clinical Studies and not the SAE form is to be completed. If there is an SAE and / or AESI associated with the pregnancy an SAE form must be completed in addition.

5.2.7.2.4 Safety monitoring and adverse events with additional information collection

- An external expert in radiology will review all MRI/radiological assessments (bone imaging). Additionally, images of a particular patient may be reviewed by other radiology or clinical experts selected by the sponsor for consultancy, if judged needed by the sponsor to assess safety of this particular patient or to support overall safety assessment.
- A blinded external expert in paediatric dentistry will review all panoramic x-rays (dental imaging). Additionally, images of a particular patient may be reviewed by other external dentist/expert in paediatric dentistry selected by the sponsor for consultancy, if judged needed by sponsor to assess safety of this particular patient or to support overall safety assessment.
- An independent SMC will conduct regular reviews of the trial safety data, with access to any data including MRI/radiological assessments, height measurements, and panoramic x-rays, as detailed in [Section 3.1](#), in [Section 5.2.5](#) and in the SMC charter.
- An independent Adjudication Committee (AC) will review all fatal cases and adjudicate all deaths to either cardiac, respiratory or other causes and will review all adverse events categorized as major adverse cardiovascular events (MACE). MACE is defined as non-fatal myocardial infarction, non-fatal stroke and cardiac death. In parallel, the Adjudication Committee/a member of the Adjudication Committee will review all dental findings of stunted growth of the dental root identified by central review to assess them to either pathological finding /stunted growth or not. Certain further dental findings on dental imaging may potentially be assessed if defined in the Adjudication Charter (dental imaging from 1199-0337 study may be included in this assessment process).

- Additional details (on top of standard AE and SAE reporting) will be collected in the eCRF for the adverse event ‘diarrhoea’ and the adverse events in the subordinate Standard MedDRA Query (SMQ) ‘Haemorrhage terms, excluding laboratory terms’.

[figure not shown]

[figure not shown]

[figure not shown]

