Total number of patients entered	Approximately 50 to 60 patients
Number of patients per treatment group	Not applicable
Diagnosis	Clinically significant fibrosing ILD
Main inclusion and exclusion criteria	
Patients who have completed the 1199-0337 (InPedILD[®]) study and did not prematurely discontinue trial treatment
 
or
 
Patients (children and adolescents ≥ 6 and ≤ 17 years old except in France (adolescents ≥ 12 and ≤ 17 years old)) with clinically significant fibrosing ILD who meet the following eligibility criteria:
 
Main inclusion criteria:
 
Evidence of fibrosing ILD on HRCT within 12 months of Visit 1, FVC % predicted $\geq 25\%$ at Visit 2 and clinically significant disease at Visit 2 based on either clinical markers of disease severity or

	
evidence of clinical progression over time.
 
Main exclusion criteria: AST and/or ALT and/or bilirubin >1.5 x ULN, and/or eGFR <30 mL/min/1.73m², and/or underlying chronic liver disease (Child Pugh A, B or C hepatic impairment) at Visit 1; significant pulmonary arterial hypertension, any cardiovascular disease excluded by protocol, history of thrombotic event within 12 months of Visit 1, bleeding risk.

Test product(s)	nintedanib
dose	
150 mg b.i.d. (300 mg daily), 100 mg b.i.d. (200 mg daily), 3x25 mg b.i.d. (150 mg daily), 2x25 mg b.i.d. (100 mg daily) or 25 mg b.i.d. (50 mg daily).
 
The dose assigned is based on patient's weight. Dose reduction is possible to manage adverse events. The lowest possible dose is 25 mg b.i.d. (50 mg daily).

mode of administration	Per os
Comparator product(s)	Not applicable
dose	Not applicable
mode of administration	Not applicable

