A SMC composed of external experts independent from the trial and selected BI non-trial team members will be established to review [REDACTED] and safety data at regular intervals to determine the safety profile and risk/benefit ratio and recommend dose modification, additional assessments (e.g. laboratory tests), appropriateness of further enrolment and continuation/modification/premature interruption of the study. The SMC will also conduct regular reviews of the trial safety data, including MRI/x-rays assessments, height measurements, and dental panoramic x-rays, as detailed in [Section 3.1](#), in [Section 5.2.5](#). Details of the SMC responsibilities and procedures are described in the SMC charter.

To determine how well the protocol inclusion criteria were able to identify the intended population, an independent Disease Review Committee (DRC) will be established to retrospectively review patient's clinical data and results of HRCT and biopsy central reading for all new patients evaluated for study participation at Visit 1. Members of the committee will be blinded to patient screening outcome. The composition of the DRC will be documented in the Trial Master File (TMF). The tasks and responsibilities will be agreed in contracts between the DRC members and the sponsor and also summarised in a DRC charter. Charter and meeting minutes will be filed in the TMF. The data will be collected at set interval and analysed after DBL 1.

An independent Adjudication Committee (AC) will review all fatal cases and adjudicate all deaths to either cardiac, respiratory or other causes, and review all adverse events categorized as MACE (see [Section 5.2.7.2.4](#) for details). In parallel, the Adjudication Committee/a member of the Adjudication Committee will review all dental findings of stunted growth of the dental root identified by central review to assess them to either pathological finding /stunted growth or not. Certain further dental findings may potentially be assessed if defined in the Adjudication Charter (dental imaging from 1199-0337 study may be included in this assessment process).

A steering committee will provide scientific advice on the clinical development program of nintedanib in the pediatric population. Tasks and responsibilities are defined in a contract.

BI has appointed a Clinical Trial Leader responsible for coordinating all required activities, in order to

- manage the trial in accordance with applicable regulations and internal SOPs,

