7.8.1.1 Adjudicated adverse events

An independent adjudication committee will review all fatal cases and adjudicate cause of death to respiratory, cardiovascular or other. The adjudication committee will also review all AEs categorised as MACE according to the definition in the adjudication charter.

In addition to standard safety analyses, the frequency of patients with AEs leading to death will be summarised by treatment, adjudicated cause of death (Cardiovascular, Respiratory or Other), and PT.

The frequency of patients with AEs categorised as MACE (that is all AEs categorised as MACE and therefore sent for adjudication) will be summarised by patient group and outcome

of adjudication (adjudicated as MACE or adjudicated as not MACE). The frequency of patients with AEs adjudicated as MACE will also be summarised by patient group and PT.

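### Protocol and SAP class a stroke death differently, and the protocol's MACE definition, read literally, counts a survived stroke but not a fatal one

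*Protocol*

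**What the plan says.** Protocol 5.2.7.2.4 gives the composite explicitly: "MACE is defined as non-fatal myocardial infarction, non-fatal stroke and cardiac death". The same section and protocol 8.7 set the committee's task for deaths; in the words of 8.7, "An independent Adjudication Committee (AC) will review all fatal cases and adjudicate all deaths to either cardiac, respiratory or other causes".

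SAP 7.8.1.1 describes the same task with a different first class: "An independent adjudication committee will review all fatal cases and adjudicate cause of death to respiratory, cardiovascular or other". The table it plans is laid out by "adjudicated cause of death (Cardiovascular, Respiratory or Other), and PT". For the composite, the SAP does not repeat or cite the protocol sentence. It says instead: "The adjudication committee will also review all AEs categorised as MACE according to the definition in the adjudication charter". It then plans a summary of patients with events categorised as MACE, split by whether the committee confirmed them, and a summary of the confirmed events by preferred term.

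Neither document defines cardiac death or cardiovascular death, and neither says where a fatal stroke belongs.

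**The concern.** A composite whose components are non-fatal MI, non-fatal stroke and a death term works only if the death term takes in the fatal form of each component. Here the death term is cardiac. A fatal MI comes back in by that route, but a fatal stroke does not on the ordinary meaning of the word. The worst outcome of a component would then be left out while the milder one counts.

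The classification of deaths matters separately. A stroke death is other under the protocol and ordinarily cardiovascular under the SAP, so the same adjudicated case could be reported in either row depending on which document the committee followed.

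This is a long-term safety trial, and the protocol treats these events as relevant. Recent thrombotic events, including stroke, and recent haemorrhagic CNS events are exclusions for new patients (3.3.3). Both stroke and haemorrhagic CNS events are among the situations in 3.3.4.1 where stopping trial drug is strongly advised, subject to investigator judgement. A reader of the report will expect the adjudicated cardiovascular tables to be complete on this point.

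**Working it through.** The plan gives no stroke rate, event count or test for this item, so the check is a comparison of definitions followed by a trace of each event type.

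**Inputs.** MACE components: protocol 5.2.7.2.4. Death classes: protocol 5.2.7.2.4 and 8.7, against SAP 7.8.1.1. Source of the analysed MACE: SAP 7.8.1.1, which points to the charter. Planned size: protocol synopsis, "Approximately 50 to 60 patients".

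**Trace, taking cardiac and cardiovascular in their ordinary sense.**

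| Event | MACE, protocol | Death class, protocol | MACE, SAP | Death class, SAP |
|---|---|---|---|---|
| Non-fatal MI | yes | not a death | per charter | not a death |
| Fatal MI | yes, as cardiac death | cardiac | per charter | cardiovascular |
| Non-fatal stroke | yes | not a death | per charter | not a death |
| Fatal stroke | no | other | per charter | cardiovascular |

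The fatal stroke row is the only one of the four in which the protocol leaves an event out of MACE or the two documents differ in substance on the death class. Any other vascular but non-cardiac death would follow the same path.

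**What the charter could do.**

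1. If it repeats the protocol's MACE and death classes, a fatal stroke is absent from the MACE table, and the committee's output does not match the SAP's cardiovascular row.
2. If it repeats the protocol's MACE but uses the SAP's death classes, the stroke appears as a cardiovascular death in one table and is missing from MACE in the next.
3. If it uses cardiovascular death in both, nothing is lost, but the charter then contradicts the protocol's explicit definition.

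None of these three is consistent with all the documents, so alignment is needed whichever applies.

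**Scale.** Assume one patient with a fatal stroke. The MACE count changes by 1, which is 1/60 = 1.7% to 1/50 = 2.0% of patients, and one death moves between the other and cardiovascular rows. The assumption of one case is for scale only.

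**The case against.** The strongest reply is that the analysed MACE is whatever the charter says. The charter has not been seen and may already cover fatal stroke. Being the only visible definition does not make the protocol sentence the one that is applied. This stands, and it is why the omission can only be called a risk.

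Second, cardiac death inside a composite named for cardiovascular events may simply be loose drafting. That is plausible, but it supports correcting the word. SAP Section 3 sends readers to the protocol for definitions of measurements and variables, so the protocol sentence is not idle.

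Third, a fatal stroke would not vanish. Every fatal case goes to the committee, deaths are tabulated by adjudicated cause and preferred term, and SAP 7.8.1 adds separate tables for serious events and events leading to death. In a trial of this size the event would be visible by name. This stands too, and limits the consequence to the MACE count and one row label.

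Some stronger readings are tempting but unsupported:

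- A reader might infer that the SAP reports a cardiovascular class nobody assigns. It does not: SAP 7.8.1.1 itself directs the committee to "adjudicate cause of death to respiratory, cardiovascular or other", against the protocol's "adjudicate all deaths to either cardiac, respiratory or other causes". The conflict is between the documents, not within the SAP.
- A reader might infer that the MACE count will be understated by some fraction. No figure follows, because the documents give no stroke counts.
- A reader might infer that deaths have already been misclassified. The documents report no deaths. The SAP history table shows only that an interim report exists.
- A reader might infer an undisclosed change of analysis. SAP Section 4 is partly redacted, so that cannot be said.

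**Conclusion.** The point holds in limited form. The protocol's stated rule, read literally, puts a survived stroke in MACE and a fatal one outside it. The protocol and SAP also give the same committee different death classes, so they disagree on where a stroke death is counted. Whether a fatal stroke would actually be missing from the MACE table depends on the charter and is not established.

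The conclusion rests on reading cardiac as not including stroke and cardiovascular as including it, since neither document defines either word. One affected patient would be 1.7% to 2.0% of the planned population. The tables concerned are descriptive, with no test attached. The primary endpoint, patients with any treatment-emergent adverse event, does not depend on adjudication or on MACE. The inconsistency is still worth removing, because these are adjudicated safety tables in a trial whose purpose is safety.

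**What to change.** Use one death classification in protocol 5.2.7.2.4 and 8.7, the adjudication charter and SAP 7.8.1.1: cardiovascular (stated to include fatal stroke), respiratory, other. Use one MACE definition in the same places: non-fatal MI, non-fatal stroke, cardiovascular death. Have SAP 7.8.1.1 state that definition or cite the aligned protocol text, so that the table can be read without the charter. Because cardiovascular death is wider than cardiac death plus fatal stroke, the charter should also say how other vascular deaths are classed.

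If any deaths have been adjudicated under the present wording, the committee should re-check them against the single rule before final database lock. Any change of class is the committee's decision and should not be made by relabelling at the analysis stage.

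The cost is a few words in three documents and, if there are such deaths, a short committee review. No new data collection is needed.
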